### 4.2 Safety endpoints

1) Incidence of adverse events and side effects

This refers to any unfavorable event occurring between the use (administration) and the end of use (administration) of this trial drug, regardless of whether or not it is related to the trial drug. During the follow-up period, information will be collected only for events for which a causal relationship cannot be rejected.

2) Laboratory test values

Hematology tests, blood biochemistry tests, and urinalysis.

### 5. Analysis set

### 5.1 Full analysis set (FAS)

The FAS was a set in which the following cases were excluded from all registered cases:

1) Examples of serious GCP violations (breach of consent acquisition, breach of contract, non-deliberation by the IRB).

- 2) Cases violating eligibility criteria, cases unblinded by non-regular procedures.
- 3) Trial drug-naive cases.
- 4) Cases with no efficacy data.

### 5.2 Per protocol set (PPS)

The PPS was a set in which the following cases were excluded from all registered cases:

1) Examples of serious GCP violations (breach of consent acquisition, breach of contract, non-deliberation by the IRB).

2) Serious protocol violations (eligibility criteria violations, serious regulatory violations related to compatible medications, serious treatment violations, assignment violations, unblinded cases due to non-regular procedures).

3) Patients who do not meet the minimum values set in the clinical trial protocol (e.g., if the percentage of drugs taken before meals (regardless of morning, afternoon, or evening) is less than 50%).

4) Patients who took less than 80% of the trial drug throughout the trial period.

5) Cases with no efficacy data.

### 5.3 Safety analysis set

The safety analysis set was a set in which the following cases were excluded from all registered cases:

1) Examples of serious GCP violations (breach of consent acquisition, breach of contract, non-deliberation by the IRB).

2) Trial drug-naive cases.

3) Cases in which all endpoints related to safety evaluation after the start of the trial cannot be used.

### 6. Statistical analysis policy

### 6.1 Significance level and confidence level

Unless otherwise specified, tests are two-sided tests with a significance level of 0.05, and the confidence interval is a two-sided confidence interval with a confidence coefficient of 95%.

### 6.2 Multiplicity adjustment

Given that this trial is a phase I/II trial, multiplicity was not considered in either pairwise comparisons or dose-response evaluations using the maximum contrast method of the response rate, which is the primary efficacy endpoint, between each dose group and the placebo group. Additionally, multiplicity of tests will not be considered when tests are repeated for secondary endpoints.

#### 6.3 Summary statistics

In this statistical analysis plan, unless otherwise specified, the quantitative summary statistics are set as the number of subjects, mean, standard deviation, minimum, median, and maximum; and the qualitative summary statistics are the number of subjects in each category and their percentages (%).

#### 6.4 Handling of time-series data

#### 6.4.1 Calculation of number of days

In this statistical analysis plan, the calculation of the number of days is standardized by the following calculation method:

administration start day onwards = target day – administration start day (day 1)+1

before administration start day = target day – administration start day

Therefore, the administration start day is day 1, the day after the start of administration is day 2, and the day before the start of administration is day -1.

#### 6.4.2 Baseline

The baseline for evaluation of the time-series data is the value observed at the most recent time point prior to the first administration of the trial drug.

#### 6.4.3 Discontinuation of trial

In this document, the terms "discontinue" and "at discontinuation" are used to mean "discontinuation of the trial" and "at the time of discontinuation of the trial," respectively. The "discontinuation of trial drug administration" will be written exactly as described.

6.4.4 Range of data adoption for evaluation periods

Table 2 shows the trial protocol-stipulated evaluation periods and the corresponding time intervals of the efficacy endpoints of histology, cytology, presence or absence of an HPV E7-specific immune response, and HPV genotype changes, as well as the safety endpoints of laboratory tests. In practice, the tests may be conducted at a time point outside the defined time interval. Therefore, the range of data adoption is defined in the rightmost column of Table 2, and the following two points are set as the policy for setting the range of data adoption in such cases:

1) For the four visits at weeks 5, 9, 16, and 24, for which laboratory test measurements are planned, there should be no overlap in the two ranges of data adoption that correspond to two adjacent visits, and no gaps in time.

2) For weeks 5, 9, and 16, the upper limit of the range of data adoption should be one week after the last day of the permissible range of visits (e.g., for week 5, the range should be until day 49, which is one week after day 42, i.e., the last day of that week).

The data obtained within the range of data adoption should be adopted as the data of the corresponding visit. For example, if histology was conducted within the range of day 85–day 133, then the results will be adopted as data at the end of the trial (16 weeks after first administration).

Evolution	Time interval	Test item		Danga	f data		
period	(according to	Histology	Cytology	HPV*	Laboratory	adoption	i data
_	clinical trial				test		

Table 2. Trial protocol-stipulated evaluation period and range of data adoption

	protocol)					
First visit		0	0			~ Day1
Administration	Day 1			0	0	~ Day1
start day						
Week 1	Day 2–7					
Week 2	Day 8–14					
Week 3	Day 15–21					
Week 4	Day 22–28					
Week 5	Day 29–42**				•	~ Day 2–49
Week 6–7	Day 36–49					
Week 8	Day 50–56					
Week 9	Day 57–77**		•		•	~ Day 50–84
Week 10–15	Day 64–105					
Week 16	Day	•	•	•	•	~ Day 85–133
	106-126**					
Week 17–23	Day 113–161					
Week 24	Day	0	0	0	0	~ Day 134
	162–182**					
At		•	•	•	•	
discontinuation						

\* HPV: HPVE7-specific immune response, HPV genotype

\*\* : Permissible range of visit

 $\circ$ : Implemented before start of administration;  $\bullet$ : Implemented after start of administration;  $\odot$ : Implemented only for cases subject to follow-up survey

If the test was conducted multiple times within the range of data adoption, including the test at the time of discontinuation of the trial, the date closest to the middle day of the protocol-specified time interval is adopted (e.g., for week 16, this is day 116, which is the middle day of the time interval of day 106–126). If there are two test dates that are the same number of days apart before and after the middle day of the stipulated time interval, the data of the latter test date is adopted. Data of laboratory tests conducted at discontinuation of the trial will also be tabulated separately as data for the evaluation period of "at time of discontinuation." However, it should be noted that the acceptance or rejection of data at the time of discontinuation of the trial also depends on the reason for discontinuation (see Section 6.6).

#### 6.5 Handling of missing values

As a general rule, missing data will not be supplemented. However, as described in Section 4.4.1, the implementation of histopathological tests at 24 weeks after the first dose (applicable cases only) for cases judged to be normal at 16 weeks after the first dose is also stipulated in cases where CIN lesion is confirmed by colposcopy. Based on these points, handling will be as follows: (1) In the cases judged to be "normal" at 16 weeks after the first dose, the data of "at week 24" will be handled as normal. (2) In the cases judged to be "CIN3" at 16 weeks after the first dose, the data of "at week 24" will be handled as CIN3. (3) In the cases with missing histopathological tests at 16 weeks after the first dose will be handled as missing data.

#### 6.6 Handling of data at discontinuation

The handling of data obtained at discontinuation when discontinuing the trial for individual subjects is shown in Table 3, in accordance with the reason for discontinuation.

Reason for discontinuation	Handling of data obtained at discontinuation
	Efficacy Safety
Cervical cancer detected at interim evaluation	Adoption
(nine weeks after first administration)	Histology at end of trial (16 weeks after first
	administration) is handled as PD
Request for withdrawal of consent from subject	Adoption
	However, non-adoption if use of data is refused
Suspension of trial because of subject	Adoption
circumstances (address relocation, change in	
physician / hospital transfer, busy schedule,	
unable to follow-up, etc.)	
Revealed after start of trial as not eligible	Exclusion from FAS Adoption
	and PPS
Judgment of discontinuation by investigator /	Adoption
sub-investigator because of occurrence of	
adverse event	
Difficult to continue treatment because of	Adoption
worsening symptoms of primary disease	
Revealed to be pregnant after start of trial	Adoption
Judged not evaluable because of significant	Adoption in FAS, Adoption
deviation from this trial protocol	exclusion from PPS

#### Table 3. Handling of data at discontinuation

Judged	difficult	to	continue	treatment	by	Adoption
investigator / sub-investigator for other reasons			other reason			

### 6.7 Handling of safety data

### 6.7.1 Adverse events / side effects

Adverse events and side effects that occur after the first administration of the trial drug are targeted.

- Number of incident cases: if multiple adverse events (side effects listed in Table in the Appendix) that correspond to the same PT code (or SOC code) occur in the same subject, they will be counted as a single case.
- Incidence proportion: calculated as the number of incident cases / number of observed cases.
- Number of occurrences: if multiple adverse events (side effects listed in Table in the Appendix) that correspond to the same PT code (or SOC code) occur in the same subject, they will be counted as a single occurrence.

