#### 3. Trial method

#### 3.1 Trial design

The trial was a placebo-controlled randomized double-blind comparative study (Phase I/II clinical trial) of four dose parallel groups: placebo, low-dose (0.5 g/administration/day), intermediate-dose (1.0 g/administration/day), and high-dose (1.5 g/administration/day).

- Dosage and dose: The subject will take three sticks of trial drug once daily before breakfast. Consecutive administration for five days constitutes one course, with a total of four courses administered from the first administration (Day 1 to Day 5), Day 8 to Day 12, Day 22 to Day 26, and Day 50 to Day 54. However, the dose on Day 1 will be administered between meals in the hospital.
- Trial period: 16 weeks. Primary evaluation at 16 weeks after first dose.
- Follow-up period: eight weeks. Pathological evaluation (biopsy) was performed 16 weeks after the first dose to avoid missing patients who had progressed to invasive cancer; if the lesion was CIN3 or lower, the patients were again evaluated pathologically 24 weeks after the first dose. If a patient was diagnosed clinically as CIN3 or more at week 16, she received standard therapy.

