### 7.4.1.1. Occurrence of adverse events and side effects

Target Safety analysis set

population:

Analysis
 For both the adverse events and side effects in each group, calculate the number of incident cases, number of occurrences, percentage of the number of cases (%), and their two-sided 95% confidence intervals for all events that

occurred, serious events, severe events (NCI-CTCAE Grade 3 or higher), and events that led to discontinuation of the trial drug. The denominator of the percentage (%) of the number of cases is the number of cases in the target population, and the Clopper–Pearson method is used to calculate the two-sided 95% confidence interval.

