7.4.1.3. Occurrence of adverse events and side effects for each symptom

Target Safety analysis set

population:

Analysis	Calculate the number of incident cases and incidence rate of adverse events
content:	(or side effects) for each group according to symptom (SOC, PT).

Definition: • If there are multiple events with the same SOC (PT when tabulating according to PT) in the same case, this is counted as one case.

7.4.1.4. Seriousness-based occurrence of adverse events and side effects for each symptomTarget Safety analysis setpopulation:

27

Analysis	· Calculate the number of incident cases and incidence rate of adverse events		
content:	(or side effects) for each group according to symptom (SOC, PT) and		
	seriousness.		
Definition:	Seriousness: non-serious; serious		
	• If there are multiple events with the same SOC (PT when tabulating according		
	to PT) in the same case, the event with the highest seriousness is used and		
	counted as one case.		
7.4.1.5. Sev	erity grade-based occurrence of adverse events and side effects		
Target	Safety analysis set		
population:			
Analysis	· Calculate the number of incident cases and incidence rate of adverse events		
content:	(or side effects) for each group according to symptom (SOC, PT) and grade.		
Definition:	• Grade: Grade 1; Grade 2; Grade 3-5 (according to CTCAE v4.0)		
	• If there are multiple events with the same SOC (PT when tabulating according		
	to PT) in the same case, the event with the highest grade is used and counted as		
	one case.		
7.4.1.6. Occ	surrence of adverse events and side effects leading to discontinuation of the trial drug		
Analysis	· Calculate the number of incident cases and incidence rate of the adverse		
content:	events (or side effects) that led to discontinuation of trial drug administration		
	among any of the four groups for each group according to symptom (SOC, PT).		
Definition:	• Adverse events leading to discontinuation of trial drug administration: adverse		
	events where the response to "Discontinuation of Study Treatment" in the		
	eCRF was "Yes"		
	• If there are multiple events with the same SOC (PT when tabulating according		
	to PT) in the same case, this is counted as one case.		
7.4.2. Lab	oratory test values		
7.4.2.1. Tab	ulation of laboratory test values		
Target	Safety analysis set		
population:			
Analysis	•Calculate summary statistics of test items of quantitative values for each group		

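### SAP 6.7.1 gives the number of adverse event occurrences the same once-per-subject rule as the number of cases, so the figure reported in 7.4.1.1 understates the number of events (minor)

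*SAP*

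**What the plan says.** Section 6.7.1 defines three quantities for adverse events and side effects.

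- **Number of incident cases:** events sharing a PT (or SOC) code that "occur in the same subject, they will be counted as a single case".
- **Incidence proportion:** incident cases divided by observed cases.
- **Number of occurrences:** under the same condition, "they will be counted as a single occurrence".

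Section 7.4.1.1 then asks, by group, for the "number of incident cases, number of occurrences, percentage of the number of cases" and confidence intervals. It does so for four pooled rows: all events, serious events, Grade 3 or higher, and events leading to discontinuation of the trial drug.

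The by-symptom analyses in 7.4.1.3 to 7.4.1.6 ask only for incident cases and an incidence rate. Their counting rule is stated for cases, for example in 7.4.1.3: "If there are multiple events with the same SOC (PT when tabulating according to PT) in the same case, this is counted as one case". No other section defines an event count that keeps repeats.

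On exposure, section 3.1 states: "Consecutive administration for five days constitutes one course, with a total of four courses administered". The courses start on Days 1, 8, 22 and 50.

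**The concern.** A table that shows both cases and occurrences normally does so because they answer different questions: how many subjects were affected, and how many events there were. Section 7.4.1.1 clearly intends two quantities, but 6.7.1 gives both the same collapsing rule. A reader of the finished table would take the occurrence column as an event total, and it would not be one.

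This has some weight here. Section 2 names confirmation of safety as an aim, and repeated dosing in four separate courses gives the same event several chances to return in one subject. Section 7.4.1.1 is also the only planned summary by group that could show event burden.

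A second problem follows. The rule names PT with SOC in parentheses and does not say which applies in a row that pools all codes. Two programmers could follow the SAP faithfully and report different numbers.

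**Working it through.** The SAP states no figure to reproduce, so the check applies the definitions.

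**Step 1. Compare the two definitions.** The condition is the same in both: more than one event, same PT (or SOC) code, same subject. The result is the same too: count one. Only the unit named at the end differs. For a single code, both counts therefore equal the number of distinct subjects with that code.

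**Step 2. Apply them to an invented event list.** There are three subjects and eight events:

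- Subject 1: diarrhoea in each of the four courses (4 events)
- Subject 2: diarrhoea once, nausea twice (3 events)
- Subject 3: headache once (1 event)

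Diarrhoea and nausea share a gastrointestinal SOC; headache falls under a nervous-system SOC.

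| Row | Cases | Occurrences under 6.7.1 | All events |
|---|---|---|---|
| PT diarrhoea | 2 | 2 | 5 |
| PT nausea | 1 | 1 | 2 |
| PT headache | 1 | 1 | 1 |
| Gastrointestinal SOC | 2 | 2 | 7 |
| Pooled, collapsed by PT | 3 | 4 | 8 |
| Pooled, collapsed by SOC | 3 | 3 | 8 |

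Within a code the two counts agree, as step 1 requires. In the pooled row the occurrence count is 4 or 3 depending on the governing level, against 8 events.

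**Step 3. Size for one PT.** Inputs from the SAP are 41 subjects per group (3.3) and four courses (3.1). The SAP gives no event rates, so I assume a probability *p* that a subject has the event in a given course. It is taken as independent between courses, with at most one event per course, and ranges from 0.05 to 0.30.

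- Expected occurrences under 6.7.1 (equal to cases): 41 × [1 − (1 − *p*)⁴]
- Expected events: 41 × 4 × *p*
- Share uncounted: 1 − (first ÷ second)

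For *p* = 0.20: 41 × (1 − 0.4096) = 24.2 counted; 41 × 4 × 0.20 = 32.8 events; 1 − 24.2/32.8 = 26%.

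| *p* | Counted under 6.7.1 | Events | Uncounted |
|---|---|---|---|
| 0.05 | 7.6 | 8.2 | 7% |
| 0.10 | 14.1 | 16.4 | 14% |
| 0.20 | 24.2 | 32.8 | 26% |
| 0.30 | 31.2 | 49.2 | 37% |

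Under these assumptions the uncounted share grows with event frequency.

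**Step 4. Check what else uses the count.** The incidence proportion in 6.7.1, the percentages and Clopper–Pearson intervals in 7.4.1.1, and the tables in 7.4.1.2 to 7.4.1.6 are all built on subjects. None uses the occurrence count, and neither does any test in the SAP.

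**The case against.** The strongest reply is that this is a drafting or translation slip in one auxiliary descriptive number. No safety proportion or interval changes, no decision rests on the count, and Appendix 2 plans listings of adverse events and side effects in which repeats may still be visible. All of that stands, and it limits the severity. It does not make the definition right: a listing is not a summary by group, and the text as written is what would be programmed.

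Three stronger readings are tempting, and the SAP does not support them.

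- *A reader might infer that the two columns of 7.4.1.1 will simply be identical.* That holds only within a single PT or SOC. The rows of 7.4.1.1 are pooled, and if PT governs, a subject with two different PTs contributes two occurrences but one case (4 against 3 in the example).
- *A reader might infer a much larger loss, for instance one counted instead of four for a subject affected in every course.* The arithmetic is right for that subject, but nothing in the SAP indicates how common such subjects would be. Nor does it plan an occurrence count by PT in which the loss would appear. The 7% to 37% range also rests on assumed rates.
- *A reader might infer that a corrected count would reveal recurrence by course or a dose relation in it.* A pooled total cannot separate one symptom returning four times from four unrelated symptoms, and it has no course dimension. It shows event burden only.

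**Conclusion.** The definition is wrong as written. Section 6.7.1 makes the number of occurrences obey the rule for cases, so the figure in 7.4.1.1 drops every same-code repeat and is ambiguous between PT and SOC in the pooled rows. The loss of repeats does not depend on which level governs.

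The size is not fixed by the SAP. The 7% to 37% range for one PT depends on the assumed per-course probability and on independence between courses. If events cluster in the same subjects, the uncounted share would be larger at a given *p*; if repeats are rare, it would be smaller.

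Severity is minor: one descriptive safety count is affected, and all subject-level results stand.

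**What to change.** In 6.7.1, define the number of occurrences as the total number of recorded adverse events (or side effects), counting every event, including repeats of the same PT or SOC in the same subject. Keep the once-per-subject rule for the number of incident cases and the incidence proportion only. This also removes the PT/SOC ambiguity in the pooled rows, because nothing is collapsed.

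The cost is one sentence in the SAP and a small change to the program for one table. The planned event listings suggest that event-level records exist, so no new data should be needed. The SAP does not show, however, whether a returning event is entered as a new record or as one continuing event, so the data-entry convention should be checked and stated in a table footnote. If the tables have already been produced, the occurrence column should be recalculated and footnoted.

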#### 6.7.2 Laboratory test values

See Appendix 1 for laboratory test items conducted in this trial.

#### 7. Analysis method

See Appendix 2 for the list of forms created in this analysis, and Appendix 3 for the software and dictionaries used.

#### 7.1 Case composition

7.1.1 Breakdown of subjects

Analysis Registered / allocated cases

target:

Analysis Calculate the following for each group, where the denominator of the percentage is content: the number of registered / allocated cases:

• Number of cases who were administered the trial drug, number of cases who were not administered the trial drug, and their percentages

• Number of cases who completed four courses of administration; number of cases who did not complete four courses of administration; number of cases who completed one, two, or three courses of administration; and their percentages

• Number of cases who completed observation during the trial period (16 weeks) and the percentage

• Number of cases who completed observation during the follow-up period (eight weeks) and the percentage

· Number of cases who discontinued the trial during the trial period or follow-up

period and the percentage

• Number of cases by reason for discontinuation. See Table 2 for classification of the reasons for discontinuation

## 7.1.2 Deviation from trial protocol

Analysis	Registered / allocated cases		
target:			
Analysis	Calculate the following for each group, where the denominator of the percentage is the		
content:	number of	Fregistered / allocated cases:	
	• Number	r of cases with the presence or absence of deviation and the percentage.	
	• Number	r of cases according to each reason for deviation.	
	The reason	ns for deviation are classified as follows:	
	1)	Deviation relating to selection / exclusion criteria	
	2)	Deviation relating to trial drug discontinuation criteria	
	3)	Deviation relating to trial drug administration method	
	4) ]	Deviation relating to concomitant drug / therapy	
	5)	Other deviation	
Remarks:	If multiple	e reasons for deviation apply to the same subject, each reason for deviation is	
	counted		
7.1.3 Analysis	set		
Target	Registered	I / allocated cases	
population:			
Analysis	Calculate	the number of cases of adoption / non-adoption and the percentage for the	
content:	FAS, PPS,	, and safety analysis set, respectively. The denominator of the percentage is	
	the numbe	er of registered / allocated cases. Also calculate the number of cases for each	
	reason for	non-adoption. The reasons for non-adoption are classified as follows:	
	• Reasons	s for non-adoption to FAS	
	1) ]	Examples of serious GCP violations (breach of consent acquisition, breach	
	of contract	t, non-deliberation by the IRB)	
	2)	Cases violating eligibility criteria, cases unblinded by non-regular	
	procedures	S	
	3) 7	Trial drug-naive cases	
	4)	Cases with no efficacy data	
	• Reasons	s for non-adoption to PPS	
	1) ]	Examples of serious GCP violations (breach of consent acquisition, breach	
	of contract	t, non-deliberation by the IRB)	
	2)	Serious protocol violations (eligibility criteria violations, serious regulatory	

violations related to compatible medications, serious treatment violations, assignment violations, unblinded cases due to non-regular procedures)

3) Patients who do not meet the minimum values set in the clinical trial protocol (e.g., the percentage of drugs taken before meals (regardless of morning, afternoon, or evening) is less than 50%)

4) Patients who took less than 80% of the trial drug throughout the trial period

5) Cases with no efficacy data

· Reasons for non-adoption to safety analysis set

1) Examples of serious GCP violations (breach of consent acquisition, breach of contract, non-deliberation by the IRB)

2) Trial drug-naive cases

3) Cases in which all endpoints related to safety evaluation after the start of the trial cannot be used

Remarks: If there are multiple reasons for non-adoption in the same subject, each reason for non-adoption is counted

